## 8.2. Setting

The study population will consist of patients with a diagnosis of hormone receptor-positive/human epidermal growth factor receptor 2-negative mBC who initiated a who initiated PB+FUL and CCI

The USON includes 1,200 affiliated physicians operating in over 470 sites of care across states and treats approximately 1 million US cancer patients annually.

**Figure 1** presents a graphical depiction of the study time periods, which are as follows:

- Study observation period: 01 February 2016 – 30 June 2020.\*
- Study identification period: 01 February 2016 – 31 December 2019.
- Index date: The date of initiation with PB+FUL or CCI during the study identification period. For PB+FUL, the date of the first administration of either drug will be used.
- Baseline: Assessment will be done for the data collected at the closest date prior to index within 30 days of index (in absolute value). Variables to be assessed at baseline are specified in **Table 2**.
- Prior medical history: Patients' available history in the iKnowMed (iKM) EHR will vary based on the length of disease and the time within the USON. The prior medical history period will end the day prior to the index date. Variables to be assessed with prior medical history are specified in **Table 2**.
- Follow-up: Patients will be followed through the end of the study observation period, date of last visit or date of death, whichever occurs first. For analysis, patients will have a potential of at least 6 months of follow-up duration; however, patients will have variable follow-up time periods, depending on their index dates and last contact dates.

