### 8.2.3. Cohort definitions and stratifications

Patients who meet the eligibility criteria described in **Sections 8.2.1-8.2.2** will be classified into the following cohorts described in **Section 8.1**.

As supported by the final sample size, each of the results tables and figures will be stratified to present the data for the following stratifications:

- Menopausal status (pre-, peri-, and post-menopausal) – post-menopausal only
- Metastases (visceral vs. non-visceral, bone only vs. non-bone only)
- Metastatic status (de novo versus relapsed/recurrent)
- Stage at diagnosis (I/II, III, IV or not documented)
- Number of metastatic sites (1, 2 and  $\geq 3$ )
- Prior adjuvant endocrine therapy (both prior to and after metastases)
- Prior adjuvant chemotherapy (both prior to and after metastases)
- Age stratifications (e.g., 18-50, 51-69,  $\geq 70$ ) also  $<65$  years and  $\geq 65$  years
- Race (White, Black, other, not documented)
- Palbociclib starting dose (75 mg, 100 mg, and 125 mg starting dose)
- Eastern Cooperative Oncology Group (ECOG) performance status score (0/1, and 2+) 90 days prior to index
- Disease-free interval from end of adjuvant treatment ( $< 12$  months,  $\geq 12$  months)

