### 8.3. Variables

**Table 2** presents the list of variables that will be considered for this study. Most data will originate from 1 of 2 sources: the iKM EHR database (structured data) or chart review (unstructured data), although some variables may be derived from these raw data sources (e.g., age from date of birth). Derived and transformed data needed for the analysis are described and presented along with the operational definitions in the table below.

For variables that are listed as being sourced from both structured and unstructured fields, chart review is recommended and, in some cases, may be required. Specifically, many of these are variables that are available in structured fields but have been found to be more reliably and comprehensively captured through chart review of unstructured fields. Other variables require information that can only be sourced through chart review (e.g., response and progression). Data elements listed as being “not reported” will be used to determine eligibility or in calculations of derived variables.

Variables described as being captured at “baseline” will be captured at the date closest to the index date initiation within 30 days (90 days for performance status). Variables described as being captured with “prior medical history” will be sourced from patients’ entire medical history within the USON prior to index treatment initiation. Other variable assessment periods are indicated below. If multiple values are available during the time period of measurement, the one closest (in absolute value) to treatment initiation will be used.

Some data elements will be captured from both iKM and chart review. Since the chart review data are expected to provide a richer source of information, if data are available from both sources for a single patient, then chart review data will supersede what is available in the structured iKM data for the final analysis.

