				
Pericardium Peritoneum Pleura Rectum Retroperitoneum Small intestine Spleen
 
Non-visceral
 
Brain Breast Cervical nodes Chest wall Eye Ipsilateral supraclavicular lymph node Leptomeninges Other parts of nervous system Skin Spinal cord
 
Bone only
 
Bone Bone marrow Skull
 
Other
 
No information
 
The above list will be confirmed or updated after chart review is complete
 
*Asymptomatic visceral disease will be captured by chart review for patients who have explicit documentation of symptoms in the EHR records. All others will be assumed to be asymptomatic.

Count of metastatic site(s)	iKM structured data + chart review (derived)	Baseline characteristic	Medical history prior to index	
The total count of metastatic site(s) at index:
 
No documentation 1 2 3 4+
 
Note, “no documentation” can indicates that metastases were not documented in the chart, not necessarily that patients did not have metastases.

Stage at diagnosis	iKM structured data	Baseline characteristic	Medical history prior to index	
Categorized as:
 
Stage 0 Stage IA Stage IB Stage IIA Stage IIB Stage IIIA Stage IIIB Stage IIIC Stage IV No information

Eastern Cooperative Oncology Group	iKM structured data	Baseline characteristic	Up to 90 days prior to index	The ECOG performance status score is a rating of a patient's disease status, daily living activities and quality of life, with low

PFIZER CONFIDENTIAL

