5.4 COVARIATES

Table 1 presents the list of variables that will be considered for this study. Most data will originate from 1 of 2 sources: the iKM EHR database (structured data) or chart review (unstructured data), although some variables may be derived from these raw data sources (e.g., age from date of birth). Derived and transformed data needed for the analysis are described and presented along with the operational definitions in the table below.

For variables that are listed as being sourced from both structured and unstructured fields, chart review is recommended and, in some cases, may be required. Specifically, many of these are variables that are available in structured fields but have been found to be more reliably and comprehensively captured through chart review of unstructured fields. Other variables require information that can only be sourced through chart review (e.g., response and progression). Data elements listed as being “not reported” will be used to determine eligibility or in calculations of derived variables.

Variables described as being captured at “baseline” will be captured at the date closest to the index date initiation within 30 days (90 days for performance status). Variables described as being captured with “prior medical history” will be sourced from patients’ entire medical history within the USON prior to index treatment initiation. Other variable assessment periods are indicated below. If multiple values are available during the time period of measurement, the one closest (in absolute value) to treatment initiation will be used.

Some data elements will be captured from both iKM and chart review. Since the chart review data are expected to provide a richer source of information, if data are available from both sources for a single patient, then chart review data will supersede what is available in the structured iKM data for the final analysis.

Table 1. Study variables and operational definitions

Variable	Source(s)	Role(s) in study	Period of measurement	Operational definition
Demographic and patient characteristics				
Patient identification number	iKM structured data	Data linkage	Study observation period	Unique patient identifier that will be used to link clinical records. This information will not be disclosed to the study sponsor.

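### The baseline window has no direction in Protocol 8.3 and SAP 5.4 but is pre-index in Protocol 8.2 and SAP 2.1.1, so an on-treatment value could serve as baseline

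*Protocol*

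**What the plan says.** The plan describes the baseline window in several places, and the SAP repeats each version.

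- **Protocol 8.2 (Setting), repeated in SAP 2.1.1.** The definition of the baseline period reads: "Assessment will be done for the data collected at the closest date prior to index within 30 days of index (in absolute value"). Direction is stated: before index.
- **Protocol 8.3 (Variables), repeated in SAP 5.4.** Variables marked as baseline are "captured at the date closest to the index date initiation within 30 days (90 days for performance status"). No direction is stated. If more than one value falls in the measurement period, "the one closest (in absolute value) to treatment initiation will be used".
- **ECOG.** The period of measurement in Protocol Table 2 and SAP Table 1 is "Up to 90 days prior to index". The stratification lists in Protocol 8.2.3 and SAP 4.4 define the ECOG strata as "performance status score (0/1, and 2+) 90 days prior to index". Both are pre-index only.
- **Other windows.** For prior medical history, Protocol 8.2 says "The prior medical history period will end the day prior to the index date". Comorbidities in Table 2 are limited to the 6 months up to and including the index date.

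The index date for PB+FUL is the first dose of whichever drug comes first, so any value dated after index is an on-treatment value.

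**The concern.** The plan gives a general definition of baseline that is pre-index and a general rule for deriving it that is not. Two programmers could each follow the text and extract different values for the same patient. No sentence excludes post-index values for variables whose period is simply marked as baseline, whereas the plan does state a direction for medical history, comorbidities and ECOG. The missing direction therefore looks like a drafting gap and not a deliberate choice.

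If the undirected rule is programmed, a measurement taken after treatment has begun can be labelled as baseline. It could then enter:

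- the description of baseline characteristics, which is primary objective 1;
- the menopausal stratum (Protocol 8.2.3, SAP 4.4);
- the propensity score, where BMI, menopausal status and ECOG are named as covariates, and the Cox model that follows, which is to include all variables (Protocol 8.7.3, SAP 7.1).

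Adjusting for a value that treatment or the early disease course may already have changed is a recognised source of bias, and a descriptive baseline table should not mix pre-treatment and on-treatment values without saying so.

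**Working it through.** The plan states no figure on this point, so the check compares the rules, counts days and applies the rules to examples.

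**Step 1. Which sentence lets post-index values in?** The sentence on closeness in absolute value only selects among values already inside the measurement period; it does not widen any window. The opening comes from the sentence before it, where the 30 days (90 for performance status) have no direction. The selection sentence then prefers a post-index value if it is nearer.

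**Step 2. Days in each window.** An undirected window of *d* days either side contains 2*d* + 1 days, of which *d* fall after index.

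| Rule | Days in window | Days after index |
|---|---|---|
| Undirected, *d* = 30 (Protocol 8.3, SAP 5.4) | 2 × 30 + 1 = 61 | 30 (30/61 = 49%) |
| Prior to index, 30 days (Protocol 8.2, SAP 2.1.1) | 30, or 31 if the index day counts | 0 |
| Undirected, *d* = 90, performance status (Protocol 8.3, SAP 5.4) | 2 × 90 + 1 = 181 | 90 (90/181 = 50%) |
| ECOG row and stratifier | 90, or 91 if the index day counts | 0 |

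These are shares of calendar days. They are not shares of patients.

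**Step 3. Examples for one patient's weight.**

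- Values on day −10 and day +3: the distances are 10 and 3. The undirected rule takes day +3; the prior-to-index rule takes day −10.
- Values on day −10, day 0 and day +3: the index-day value has distance 0 and is chosen under the undirected rule. Whether day 0 counts as prior to index is not stated, so the other rule could give day 0 or day −10.
- A value on day +3 only: the undirected rule uses it; the prior-to-index rule leaves the weight missing.

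An on-treatment value is therefore used only when there is no index-day value and the nearest value lies after index.

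**Step 4. Which variables are exposed?** Only those whose period in Table 2 is marked as baseline. Among these, the ones that can change over time are mainly weight (hence BMI), menopausal status and smoking. Comorbidities and items from prior medical history have their own pre-index windows. ECOG has its own pre-index row, so it is exposed only if the parenthesis on performance status, "within 30 days (90 days for performance status"), is taken to override that row.

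**The case against.** The strongest reply is that Protocol 8.2 and SAP 2.1.1 are the dedicated definition of baseline and state the direction, so the wording in Protocol 8.3 and SAP 5.4 is only shorthand for it. The absolute-value phrase in that definition also has a harmless reading: a date before index gives a negative difference, and the phrase may mean only that the distance is at most 30 days. This is a fair reading, and the definition need not contradict itself. It does not settle the matter, because the derivation text is what a programmer would follow, it gives no direction, and nothing says which text takes precedence.

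Three stronger readings are tempting, and the documents do not support them.

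- **That post-index values will be picked often.** A reader might infer this because inclusion criterion 6 requires at least two visits after index, detected by vital signs, while no criterion requires a visit before it. But those visits have no required time span and may fall outside 30 days. The Table 2 row on additional visits lets a death record count towards the requirement. The text also presumes an index visit, and an index-day value wins at distance zero.
- **That the ECOG strata are contaminated.** The stratifier is explicitly pre-index in both documents, as is the ECOG row.
- **That the bias can be given as a hazard ratio.** Any such figure needs an assumed share of post-index ECOG values and an assumed worsening among patients about to die. Neither is in the documents, and the second builds the inflation in.

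It also stands that the primary and secondary objectives are descriptive or single-cohort Kaplan-Meier analyses. The comparative part that would use the propensity score is partly redacted, so its weight in the study cannot be judged from here.

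**Conclusion.** The inconsistency is real, appears in both documents and is not resolved by the SAP. Under the undirected wording, a patient with no index-day value and a nearer post-index value would have an on-treatment measurement recorded as baseline. The exposure is mainly to weight/BMI, menopausal status and smoking, and to ECOG only if the general sentence overrides its own row.

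The size is unknown, because no document says how many patients lack an index-day value or have their nearest value after index. It is probably small. That is a judgement, resting on index-day values taking precedence, on the few variables exposed, and on the expectation that most of them change little within 30 days. The point is a wording conflict that permits an avoidable bias. It is not evidence that the results will be biased.

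**What to change.** Use one rule in Protocol 8.2, 8.3 and Table 2, and in SAP 2.1.1, 5.4 and Table 1:

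- Baseline is the last value on or before the index date, within 30 days (90 days for ECOG).
- If there is none, the variable is coded as no information.
- The absolute-value phrase is deleted.
- It is stated that index-day values count as baseline.

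The cost is a change of wording and of one derivation. A patient with values on both sides of index simply switches to the earlier one. A patient whose only value in the window is post-index becomes no information. BMI, menopausal status, smoking and ECOG already have that category, and SAP 6 reports missing values without imputing them. The number of such patients cannot be predicted from the documents, so it should be reported for each variable.

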**Table 2. Study variables and operational definitions**

Variable	Source(s)	Role(s) in study	Period of measurement	Operational definition
Demographic and patient characteristics				
Patient identification number	iKM structured data	Data linkage	Study observation period	Unique patient identifier that will be used to link clinical records. This information will not be disclosed to the study sponsor.
Medical record number (MRN)	iKM structured data	Data linkage	Study observation period	Unique patient identifier that will be used to link clinical records. This information will not be disclosed to the study sponsor.
Clinical trial participation	iKM structured data + chart review	Eligibility criteria	Follow-up	Patients will be confirmed as not being enrolled in interventional clinical trials (patients in only observational studies will be retained, if applicable) in the USON during the study observation period. If participation (on any trial other than observational only, if applicable) is detected, the patient will be excluded.
Other cancer diagnosis	iKM structured data + chart review	Eligibility criteria	Prior medical history + study observation period	Patients will be confirmed as having no additional primary or secondary malignancies prior to and after the index date. Patients with a secondary diagnosis or receipt of treatment indicated for another primary cancer will be excluded.
Hormone receptor status	iKM structured data + chart review	Eligibility criteria; Baseline characteristic	Prior medical history	Patients who have a documented hormone receptor-positive status, either estrogen and/or progesterone, will be included in the study. The proportions of patients who are estrogen or progesterone receptor-positive will be reported.
Human epidermal growth factor receptor 2-negative status	iKM structured data + chart review	Eligibility criteria	Prior medical history	Patients who have a documented human epidermal growth factor receptor 2-negative status will be included in the study.
Prior treatment	iKM structured data + chart review	Eligibility criteria	Prior medical history	Patients will be excluded if they have evidence of prior treatment with other CDK 4/6 inhibitors in the advanced or metastatic setting.
Additional visits	iKM structured data	Eligibility criteria	Follow-up	To capture a sample of patients with longitudinal records, patients will be required to have 2 records of either additional visits following the index date visit and/or a record of death prior to the end of the study follow-up period. Visits are defined as physical encounters with the practice, detected by vital sign records. There will be no distinction made, for purposes of inclusion, between patients that have an additional USON visit and those with a record of death. There is no minimum or maximum requirement on time from index date to these qualifying events.
Sex	iKM structured data +	Baseline characteristic	Prior medical history	Patients will be categorized as: Male Female

PFIZER CONFIDENTIAL

## Palbociclib (IBRANCE)

## Study Number A5481128 NON-INTERVENTIONAL STUDY PROTOCOL

Protocol Version 2, August 30, 2021

	chart review			
Date of birth	iKM structured data	Eligibility; Data linkage; Baseline characteristic	Prior medical history	Patient's date of birth as recorded in iKM. This information will not be disclosed to the study sponsor.
Age	iKM structured data (derived)	Eligibility; Baseline characteristic	Baseline	Patient's age (in years) at the date of diagnosis, which will be calculated as the integer of [(diagnosis date – date of birth + 1) / 365.25]. Patients aged less than 18 years at the initial recorded diagnosis of mBC will be excluded from the study.
Age groups	iKM structured data (derived)	Baseline characteristic	Baseline	Multiple age categories will be created based on the continuous age data: Age (<18 years, 18-50 years, 51-70 years, $\geq$ 71 years) No information
Race	iKM structured data	Baseline characteristic	Prior medical history	Categorized as: White or Caucasian Black or African American Asian Native American Other No information The specific categories outside of White/Caucasian and Black/African American will be confirmed after reviewing sample sizes and the added value to the study with McKesson's Privacy and Compliance team.
Height	iKM structured data	Baseline characteristic	Baseline	Patient's height in meters.
Weight	iKM structured data	Baseline characteristic	Baseline	Patient's weight in kilograms.
Body mass index (BMI) at index date	iKM structured data (derived)	Baseline characteristic	Baseline	BMI = Weight (in kilograms)/(Height (in meters))  Based on the resulting BMI values, patients will then be categorized as underweight (BMI < 18.5), normal (BMI 18.5 – 24.9), overweight (BMI 25 – 29.9), obese (BMI $\geq$ 30) or no information (missing height or weight data).
Smoking history	iKM structured data	Baseline characteristic	Baseline	Categorized as: Never smoked Current smoker Former smoker No information
Family history of cancer	Chart review	Baseline characteristic	Prior medical history	Categorized as: Yes No
Menopausal status	iKM structured data + chart review	Baseline characteristic	Baseline	Categorized as documented by physicians: Pre-menopausal Peri-menopausal Post-menopausal No information

PFIZER CONFIDENTIAL

Menopausal type	Chart review	Baseline characteristic	Prior medical history	If patients were menopausal, whether it was natural or induced and, if induced, the method (luteinizing hormone-releasing hormone [LHRH] suppression, surgical, other).
Healthcare setting and provider characteristics				
Practice location	iKM structured data (derived)	Baseline characteristic	Baseline	
The US census region of the USON clinic where the patient received care at the index visit:
 
Midwest: Illinois, Indiana, Michigan, Ohio, Wisconsin, Iowa, Kansas, Minnesota, Missouri, Nebraska, North Dakota and South Dakota
 
Northeast: Connecticut, Maine, Massachusetts, New Hampshire, Rhode Island, Vermont, Pennsylvania, New Jersey and New York
 
South: Delaware, Florida, Georgia, Maryland, North Carolina, South Carolina, Virginia, Washington D.C., West Virginia, Alabama, Kentucky, Mississippi, Tennessee, Arkansas, Louisiana, Oklahoma and Texas
 
West: Arizona, Colorado, Idaho, Montana, Nevada, New Mexico, Utah, Wyoming, California, Oregon and Washington State
 
Missing clinic values will be captured in a "no information" category.
 
Some of the regions may need to be collapsed if there are small sample sizes (e.g., South versus non-South). This determination will be confirmed after reviewing sample sizes and the added value to the study with McKesson's Privacy and Compliance team.

				CCI
Practice size	iKM structured data (derived)	Baseline characteristic	1/1/2018 – 12/31/2018	
The number of patients seen at the USON clinic where the patient receive care for his/her index visit in the year 2018:
 
<50 patients/ year 50-99 patients/year 100-149 patients/year ≥ 150 patients/year

Physician BC patient volume	iKM structured data (derived)	Baseline characteristic	1/1/2018 – 12/31/2018	
The number of BC patients seen by the physician who provided care for the patient's index visit in the year 2018:
 
<10 patients/ year 11-49 patients/year ≥ 50 patients/year

Physician specialty	iKM structured data	Baseline characteristic	Baseline	
Specialty of the physician who provided care for the patient's index visit:
 
Hematology & medical oncology Internal medicine Other

				Not documented
iKM use at practice location	iKM structured data	Eligibility criteria	Baseline	Patients who are treated at USON sites that utilize the full EHR capacities of iKM for their index visit will be eligible for participation in the study; otherwise, patients will be excluded.
Data accessibility	iKM structured data	Eligibility criteria	Baseline	Patients whose data are accessible for research purposes will be eligible for participation in the study; otherwise, patients will be excluded.
Disease characteristics				
Date of initial BC diagnosis	iKM structured data + chart review	Eligibility criteria, Baseline characteristic	Medical history prior to index	
To assess BC diagnoses that occurred prior to index, patients' available medical history in iKM will be searched. The completeness of this history will vary based on the length of disease and the time within the USON. Records may also be incomplete for patients with an initial BC diagnosis that occurred outside of the USON.
 
Diagnosis of BC will be determined through a review of iKM's discrete diagnosis and histology fields, which are populated during the routine course of care (International Classification of Diseases [ICD] codes will not be used).
 
If no initial diagnosis date is documented, the first recorded diagnosis date in iKM will be used. This date will be used in calculations, not reported separately.
 
Patients without a recorded diagnosis of BC will be excluded from the study.

Date of mBC disease diagnosis	iKM structured data + chart review	Eligibility criteria, Baseline characteristic	Medical history prior to index	
Date of first recorded diagnosis of metastatic disease within the EHR. Patients will be qualified initially based on the date identified in the structured data; this will be confirmed during chart review among patients selected for chart review. Ultimately, the primary source will be the chart if available.
 
Patients without recorded evidence of metastatic disease will be excluded from the study.
 
Structured data will confirm the patient as metastatic and as available, indicate the earliest associated date of any of these criteria:
 
 
1) Stage IV disease
 
2) Tumor, Node, Metastasis (TNM) stage with M value of 1
 
3) Record of location of metastatic disease
 
4) Current or prior disease status containing reference to metastatic disease
 

Time since initial BC diagnosis	iKM structured data + chart review (derived)	Baseline characteristic	Medical history prior to index	The duration of time, in weeks, between the date of BC diagnosis and presentation of metastatic disease will be calculated for each patient and summarized as the mean ( $\pm$ SD) and median (range) of values. The number of patients with available data will be reported.

				Date of BC diagnosis and presentation of metastatic disease will be determined as defined above.
Time since mBC diagnosis	iKM structured data + chart review (derived)	Baseline characteristic	Medical history prior to index	The duration of time, in weeks, between the index date and presentation of metastatic disease will be calculated for each patient and summarized as the mean ( $\pm$ SD) and median (range) of values. The number of patients with available data will be reported. Presentation of metastatic disease will be determined as defined above.
Distant metastatic site(s)	iKM structured data + chart review	Baseline characteristic	Medical history prior to index	Baseline metastatic location(s) will be identified and categorized as: Bone (single) Bone (multiple) Brain Liver (single) Liver (multiple) Lung (single) Lung (bilateral) Lung (pleural effusion) Lymph nodes (regional) Lymph nodes (distant) Ovary Other No information Note, "no information" can indicate that metastases were not documented in the chart, not necessarily that patients did not have metastases.
Endocrine sensitivity at 12 months	iKM structured data	Baseline characteristic	Baseline	Patients who experienced relapse more than 12 months of completing adjuvant endocrine therapy will be considered to be endocrine sensitive; those who relapse in less than 12 months, endocrine resistant.
Endocrine sensitivity at 24 months	iKM structured data	Baseline characteristic	Baseline	Patients who experienced relapse more than 24 months of completing adjuvant endocrine therapy will be considered to be endocrine sensitive; those who relapse in less than 24 months, endocrine resistant.
Visceral/non-visceral status	iKM structured data + chart review (derived)	Baseline characteristic	Medical history prior to index	Categorized as: Visceral (asymptomatic or symptomatic*) Adrenal gland Bronchus Cervix Esophagus Gastrointestinal tract Genital organ Intestinal tract Kidney Large intestine Liver Lung Mediastinum Omentum Other respiratory organ Other urinary organ Ovary Pancreas

PFIZER CONFIDENTIAL

				
Pericardium Peritoneum Pleura Rectum Retroperitoneum Small intestine Spleen
 
Non-visceral
 
Brain Breast Cervical nodes Chest wall Eye Ipsilateral supraclavicular lymph node Leptomeninges Other parts of nervous system Skin Spinal cord
 
Bone only
 
Bone Bone marrow Skull
 
Other
 
No information
 
The above list will be confirmed or updated after chart review is complete
 
*Asymptomatic visceral disease will be captured by chart review for patients who have explicit documentation of symptoms in the EHR records. All others will be assumed to be asymptomatic.

Count of metastatic site(s)	iKM structured data + chart review (derived)	Baseline characteristic	Medical history prior to index	
The total count of metastatic site(s) at index:
 
No documentation 1 2 3 4+
 
Note, “no documentation” can indicates that metastases were not documented in the chart, not necessarily that patients did not have metastases.

Stage at diagnosis	iKM structured data	Baseline characteristic	Medical history prior to index	
Categorized as:
 
Stage 0 Stage IA Stage IB Stage IIA Stage IIB Stage IIIA Stage IIIB Stage IIIC Stage IV No information

Eastern Cooperative Oncology Group	iKM structured data	Baseline characteristic	Up to 90 days prior to index	The ECOG performance status score is a rating of a patient's disease status, daily living activities and quality of life, with low

PFIZER CONFIDENTIAL

(ECOG) performance status				
scores indicating greater functioning than high scores:
 
0 1 2 ≥3
 
No information
 
Karnofsky performance status is a similar measure and will be converted to ECOG using the methodology outlined below.
 
  
 Karnofsky Performance Status	ECOG Performance Status	ECOG Performance Status Description	
   
 100	0	Fully active	
 
 80, 90	1	Restricted in physically strenuous activity	
 
 60, 70	2	Ambulatory and capable of self-care but unable to work	
 
 40, 50	3	Capable only of limited self-care	
 
 10, 20, 30	4	Completely disabled	
 
 0	5	Dead	
  
	Karnofsky Performance Status	ECOG Performance Status	ECOG Performance Status Description	100	0	Fully active	80, 90	1	Restricted in physically strenuous activity	60, 70	2	Ambulatory and capable of self-care but unable to work	40, 50	3	Capable only of limited self-care	10, 20, 30	4	Completely disabled	0	5	Dead
Karnofsky Performance Status	ECOG Performance Status	ECOG Performance Status Description																							
100	0	Fully active																							
80, 90	1	Restricted in physically strenuous activity																							
60, 70	2	Ambulatory and capable of self-care but unable to work																							
40, 50	3	Capable only of limited self-care																							
10, 20, 30	4	Completely disabled																							
0	5	Dead																							
Comorbidities	Chart review	Baseline characteristic	6 months prior to index	
Comorbidities documented within 6 months prior to or on the index date will be captured and summarized as:
 
Atrial fibrillation Bradyarrhythmia Cerebrovascular disease Congestive heart failure Chronic pulmonary disease Connective tissue disease Dementia Diabetes with end organ damage Diabetes without end organ damage Depression Electrolyte abnormalities Hemiplegia HIV/AIDS Hyperlipidemia Hypertension Infection Leukemia Long QT syndrome (congenital) Long QT syndrome (drug induced) Lymphoma Metastatic solid tumor (other than breast cancer) Mild liver disease Moderate to severe renal disease Myelosuppression Myocardial infarction Peptic ulcer disease
																					

				Peripheral vascular disease Tachycardia Stroke Unstable angina Venous thromboembolism (pulmonary embolism or deep vein thrombosis)
Disease histology	iKM structured data	Baseline characteristic	Baseline	Categorized as: Ductal Lobular Mixed Metaplastic Tubular Mucinous Other No information
Breast cancer gene (BRCA) 1/2 status	Chart review	Baseline characteristic	Medical history prior to index	Categorized as: Positive Negative No information
Estrogen receptor 1 gene (ESR1) status	Chart review	Baseline characteristic	Medical history prior to index	Categorized as: Positive Negative No information
Next generation sequencing (NGS) status	Chart review	Baseline characteristic	Medical history prior to index	Categorized as: Positive Negative No information
Treatment characteristics				
Prior adjuvant hormonal treatment	iKM structured data + chart review	Treatment characteristics	Medical history prior to index	The proportion of patients with prior adjuvant hormonal treatment for breast cancer prior to the index treatment.
Prior neo-adjuvant/adjuvant chemotherapy	iKM structured data + chart review	Treatment characteristics	Medical history prior to index	The proportion of patients with prior neo-adjuvant/adjuvant chemotherapy for breast cancer prior to the index treatment.
Prior metastatic hormonal treatment	iKM structured data + chart review	Treatment characteristics	Medical history prior to index	The proportion of patients with prior metastatic hormonal treatment for breast cancer prior to the index treatment.
Adjuvant treatment end dates	iKM structured data + chart review	Treatment characteristics	Medical history prior to index	Date of adjuvant treatment discontinuation.
Disease-free interval	iKM structured data + chart review (derived)	Treatment characteristics	Medical history prior to index	The duration (in weeks) between discontinuation of adjuvant therapy and the start of treatment for metastatic disease. The number of patients with available data will be reported.  Findings will be summarized as the mean ( $\pm$ SD) and median (range) of values, along with

